The next cohort of 2 patients will not begin treatment until the last patient in the current cohort has reached day 21. Each new cohort of 2 patients will be assigned by the study statistician ([name] email: [contact]). The CRM assumes the working dose-toxicity model or power model. The probability (toxicity at d_i) = $p_i^{\exp(\alpha)}$ for each dose level i . The parameter α is distributed a priori as a normal random variable with mean 0 and variance 2. After simulation, a variance of 2 was predicted to balance both patient safety and accuracy. Pre-specified constants p_i for each dose are 1st determined by using the skeleton estimates at the beginning of the trial. After initiation of the trial and collection of events, the unknown parameter α is continuously updated. Calculation of posterior means of probability of toxicity from dose level i are calculated from Bayes theorem using the likelihood function based on a binomial distribution for the binary outcome of toxicity. After calculation of these means, each new cohort is assigned to the dose with an estimated toxicity probability closest to the pre-specified target toxicity of 25%.

Eventually the MTD will be identified when the total sample size of 20 patients is exhausted.

The dose limiting toxicity (DLT) is defined as any of the following occurring by day 21 after the 1st dose of hCG.

- In males and females: Grade 2-4 thromboembolic event (CTCAE v4)
- In males and females: Grade 3-4 ascites (CTCAE v4)
- Specific to females: Ovarian hyperstimulation syndrome, defined as the rapid development of enlarged, cystic, painful ovaries

Software within the BMA-CRMSimulator Version 2.1.0, downloaded from the MD Anderson biostatistics department website, will be used to calculate the posterior means of the toxicity probabilities for all of the doses under consideration:

<http://biostatistics.mdanderson.org/SoftwareDownload>. Dose escalation of more than one level is not permitted with this design.

Phase I component: Estimating the MTD of hCG for Arm 2B

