The phase I design for Arm2B (steroid-refractory aGVHD) is similar to Arm 1 and Arm 2B. The goal for CRM is to identify the dose level which corresponds to the desired toxicity rate of 30% or less. We are choosing a lower target toxicity than would be chosen under the standard design. A standard “3+3” design will often choose a dose with corresponding to a toxicity rate of 33% or lower. The trial will stop if the posterior probability (that the lowest dose is more toxic than the target dose) is 0.90.

Dose Level	hCG Dose
-2**	125 USP hCG/875 pg EGF/m ²
-1*	250 USP hCG/1,750 pg EGF/m ²
1	500 USP hCG/3,500 pg EGF/m ²
2	1,000 USP hCG/7,000 pg EGF/m ²
3	2,000 USP hCG/14,000 pg EGF/m ²
4	3,500 USP hCG/24,500 pg EGF/m ²
5	5,000 USP hCG/35,000 pg EGF/m ²

*Dose level -1 (250 USP hCG/1,750 pg EGF/m²) will be used only if Dose Level 1 (500 USP hCG/3,500 pg EGF/m²) proves too toxic.

**Dose level -2 (125 USP hCG/875 pg EGF/m²) will be used only if Dose Level -1 (250 USP hCG/1,750 pg EGF/m²) proves too toxic.

Initial estimates of toxicity or the “skeleton” estimates are given by the clinicians. The estimates of toxicity for Arm 1 and Arm2 are listed as 1%, 2%, 5%, 10%, 15%, 20% and 25% for the 7 dose levels, respectively. The 1st 2 patients will be enrolled in dose level 1. The next cohort of 2 patients will not begin treatment until the last patient in the current cohort has reached day 21. Each new cohort of 2 patients will be assigned by the study

statistician ([name] email: [contact]). With same calculation described in Arm 1 and Arm 2A, each new cohort is assigned to the dose with an estimated toxicity probability closest to the pre-specified target toxicity of 30%. DLT has the same definition as the other two arms.

Operating Characteristics for Phase I (Arm 1 and Arm 2A)

Operating characteristics are calculated by BMA-CRMSimulator for two different scenarios, one in which the “true” probabilities of DLTs are the same as those specified by the clinicians and one in which the “true” probabilities of DLTs are much higher than expected. [Table 2](#) shows that there is a 88% chance of selecting the maximum dose of 2,000 USP hCG/14,000 pg EGF/m², which is closest to our target toxicity of 25%. [Table 3](#) shows that there is a 11% chance of stopping the study or a 28% chance of selecting the dose associated with a 25% toxicity rate.

Table 2. Simulations based on “true” probabilities equal to initial skeleton estimates.

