Dose	Actual probability in theory of having a DLT at each dose	Probability of Selecting the specified dose given the probabilities of having a DLT listed in the 2nd column	Estimated Number of subjects treated at each dose level during the study
125 USP hCG/875 pg EGF/m ²	0.01	0.00	0.2
250 USP hCG/1,750 pg EGF/m ²	0.02	0.00	0.3
500 USP hCG/3,500 pg EGF/m ²	0.05	0.01	2.9
1,000 USP hCG/7,000 pg EGF/m ²	0.10	0.11	3.9
2,000 USP hCG/14,000 pg EGF/m ²	0.20	0.88	12.7

Table 3. Simulations based on “true” probabilities equal to excessively high toxicity.

Probability of stopping: 11%

Dose	Actual probability in theory of having a DLT at each dose	Probability of Selecting the specified dose given the probabilities of having a DLT listed in the 2nd column	Estimated Number of subjects treated at each dose level during the study
125 USP hCG/875 pg EGF/m ²	0.20	0.29	6.2
250 USP hCG/1,750 pg EGF/m ²	0.25	0.28	3.7
500 USP hCG/3,500 pg EGF/m ²	0.35	0.22	5.2
1,000 USP hCG/7,000 pg EGF/m ²	0.45	0.09	2.3
2,000 USP hCG/14,000 pg EGF/m ²	0.55	0.01	1.0

Operating Characteristics for Phase I (Arm 2B)

Operating characteristics are calculated by BMA-CRMSimulator for two different scenarios, one in which the “true” probabilities of DLTs are the

same as those specified by the clinicians and one in which the “true” probabilities of DLTs are much higher than expected. [Table 4](#) shows that there is a 78% chance of selecting the maximum dose of 5,000 USP hCG/35,000 pg EGF/m², which is closest to our target toxicity of 30%. [Table 5](#) shows that there is a 11% chance of stopping the study or a 29% chance of selecting the dose associated with a 30% toxicity rate.

Table 4. Simulations based on “true” probabilities equal to initial skeleton estimates.

Dose	Actual probability in theory of having a DLT at each dose	Probability of Selecting the specified dose given the probabilities of having a DLT listed in the 2nd column	Estimated Number of subjects treated at each dose level during the study
125 USP hCG/875 pg EGF/m ²	0.01	0.00	0.2
250 USP hCG/1,750 pg EGF/m ²	0.02	0.00	0.0
500 USP hCG/3,500 pg EGF/m ²	0.05	0.00	2.3
1,000 USP hCG/7,000 pg EGF/m ²	0.10	0.02	2.9
2,000 USP hCG/14,000 pg EGF/m ²	0.15	0.07	3.1
3,500 USP hCG/24,500 pg EGF/m ²	0.20	0.14	2.9
5,000 USP hCG/35,000 pg EGF/m ²	0.25	0.78	8.6

Table 5. Simulations based on “true” probabilities equal to excessively high toxicity.

Probability of stopping: 11%

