13.2 Sample Size Consideration

Resulting from laboratory studies conducted on the first several patients on this study, the investigative team plans to test higher doses in steroid-refractory patients with aGVHD (separating of Arms into 2A and 2B). This necessitates expanding the number of participants treated on the arms as described below:

Arm 1 Treated Patients	Arm 2A Treated Patients	Arm 2B Treated Patients
Level 1: N = 2, DLT = 0	Level 1: N = 1, DLT = 0	Level 1: N = 1, DLT = 0
Level 2: N = 2, DLT = 0	Level 2: N = 0, DLT = 0	Level 2: N = 2, DLT = 0
Level 3: N = 6, DLT = 0	Level 3: N = 3, DLT = 0	Level 3: N = 4, DLT = 0
Enroll 10 more patients Next dose level 3: N = 2	Enroll 16 more patients Next dose level 3: N = 2	Enroll 13 more patients Next dose level 4: N = 2

- The next dose was calculated with R package “dfcrm”.
- The next dose for Arm 2B was dose level 5, but restrict the dose jump, so the next dose will be dose level 4.

We now anticipate recruitment of 20 participants in each of the 3 arms to complete phase I.

In phase I, based on resources, the maximum number of allowable evaluable patients is 20 for each arm (total of 60 for all three arms). The simulations show it should be sufficient and safe to define the MTD for future efficacy trials.

For Arm 1 or 2A, if fewer than 13 patients are enrolled at the MTD, the phase II extension trial using Simon's two-stage Minmax design will require 26 patients to test the null hypothesis that the response rate at day 28 is <40% versus the alternative that the response rate is $\geq 65\%$ after assuming 80% power and a significance level of 0.05 and using a maximum of 26 patients. We will choose the rule that minimizes the expected sample size giving a true response rate equivalent to the null hypothesis. We expect that for each arm, phase I and II will require approximately 33 patients due to use of patients from the phase I trial in the phase II extension ([table 2](#) shows about 13 patients will be treated under MTD). But the sample size for each

arm could be as high as 44 when only two patients were treated at MTD in phase I. Therefore we expect the sample size of the phase I/II study for Arm 1 and Arm 2A will be 66 to 88 patients.

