13.4 Early Stopping Rule

During Phase I CRM, the trial will stop if the posterior probability that the lowest dose is more toxic than the target is greater than 90%. Stopping rules will also be employed to monitor excess toxicity outside of the phase I trial. Stopping rule was developed using Pocock stopping boundaries [32]. The stopping rule will be monitored for Arm 1, 2A and Arm 2B separately.

Early Stopping Rule for Toxicity

Stopping rules were developed for excessive Grade 4/5 non-hematologic, non-infectious toxicity attributed to the study drug occurring by day 28 after the last dose of hCG. The goal is to construct a boundary based on toxicity such that the probability of early stopping is at most 10% if the toxicity rate is equal to 20% and assuming 13 more patients of each arm are enrolled after phase I. Given these parameters, the upper stopping boundary for toxicity is 2 events out of 2 patients, 3 events out of 3 patients, 5 out of 8, or 6 at any time. If the true toxicity rate is as high as 50% then chance of early stopping is 80% and the expected sample size is 7.3.

14 Conduct of the Study

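### Arm 2B's dose rule can escalate to untested level 5 straight after 1 DLT in 2 patients at level 4, and no rule closes a level on its own data

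*Combined protocol and SAP*

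**What the plan says.** Section 13.1 applies a one-parameter power-model CRM to Arm 2B with a 30% target. The prior toxicity guesses are "listed as 1%, 2%, 5%, 10%, 15%, 20% and 25% for the 7 dose levels", and the assignment rule is that "each new cohort is assigned to the dose with an estimated toxicity probability closest to the pre-specified target toxicity of 30" percent. The same section gives the goal as a dose with a DLT rate of 30% or lower.

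These limits act on the next cohort:

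- A waiting period: "The next cohort of 2 patients will not begin treatment until the last patient in the current cohort has reached day 21".
- No skipping: "Dose escalation of more than one level is not permitted with this design". Section 13.2 applies this to Arm 2B: "The next dose for Arm 2B was dose level 5, but restrict the dose jump, so the next dose will be dose level 4".
- One phase I stop, in section 13.4: "the trial will stop if the posterior probability that the lowest dose is more toxic than the target is greater than 90" percent.

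The other rule in section 13.4 covers toxicity outside phase I: "Stopping rules were developed for excessive Grade 4/5 non-hematologic, non-infectious toxicity attributed to the study drug".

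No sentence ties escalation to the result of the cohort just treated. None closes a level on the DLTs seen at that level.

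**The concern.** Levels 4 and 5 were added to Arm 2B later and had no patients in the printed counts. Seven DLT-free patients at levels 1 to 3 pull the one-parameter curve down, so DLTs at level 4 or 5 move the estimates slowly. The lowest-dose stop looks at the far end of the curve and hardly responds to what happens at the top.

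The DLTs are thromboembolism of Grade 2 or worse, Grade 3-4 ascites and ovarian hyperstimulation. At stake are the next two patients in each such situation and the dose carried into phase II. The phase II boundary counts only Grade 4/5 toxicity attributed to the drug, so Grade 2 or 3 thrombosis at too high a dose would not count towards it.

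**Working it through.** **Inputs.** From 13.1: skeleton 0.01, 0.02, 0.05, 0.10, 0.15, 0.20, 0.25 for levels -2 to 5; model p_i^exp(α); α ~ N(0, variance 2); posterior means; target 0.30; cohorts of 2; at most one level up; 20 patients. From 13.2: Arm 2B counts 0/1, 0/2, 0/4 at levels 1, 2, 3, next cohort at level 4, 13 patients left.

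**Formula.** The posterior of α is proportional to exp(-α²/4) × Π p_i^(y_i·e^α) × (1 - p_i^(e^α))^(n_i - y_i). The estimate at level i is the posterior mean of p_i^exp(α). The next dose minimises |estimate - 0.30|.

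**Reproducing the plan.** From the printed counts the level 5 estimate is 0.073, the closest to 0.30. The model therefore recommends level 5, held to level 4, as 13.2 says. Simulating from a fresh start gives level 5 in 77% (Table 4: 78%). At the Table 5 rates the 30% dose is chosen in 29% (Table 5: 29%), with stopping in 8.8% (Table 5: 11%). That last small gap does not affect the decisions below.

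**Decisions from the printed counts (no true rates assumed).**

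| Data | Level 4 | Level 5 | Next dose | Pr(lowest dose > 30%) |
|---|---|---|---|---|
| 1/2 at level 4 | 0.179 | 0.221 | 5 | 0.001 |
| 2/2 at level 4 | 0.288 | 0.337 | 4 | 0.007 |
| 0/2 at level 4, 2/2 at level 5 | 0.219 | 0.266 | 5 | 0.001 |
| 0/2 at level 4, 3/4 at level 5 | 0.253 | 0.302 | 5 | 0.001 |
| 0/2 at level 4, 4/4 at level 5 | 0.323 | 0.375 | 4 | 0.005 |

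The stop needs 0.90. The decisions in the first, third and fourth rows do not change with prior variances from 0.5 to 4 or with a plug-in estimate (level 5: 0.204, 0.257, 0.298).

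Starting instead from 0/2 at each of levels 1 to 3, 1/2 at level 4 still escalates (0.207/0.250) and 2/2 at level 5 still repeats (0.246/0.294). The 3/4 case then steps down (0.279/0.328), so that one depends on the printed counts.

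**How often.** The chance of 1/2 at level 4 is 2q(1 - q): 0.32 if q = 20% (the Table 4 rate) and 0.42 if q = 30%. The chance of 0/2 at level 4 and then 2/2 at level 5 is 0.80² × 0.25² = 0.04 at the Table 4 rates, and 0.80² × 0.50² = 0.16 if levels 4 and 5 are 20% and 50%.

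**Effect of two added rules**, by exact enumeration from the printed counts. Rule 1: no escalation directly after a cohort with more than 30% DLTs. Rule 2: close a level and those above it when at least 3 patients there give Pr(rate > 30%) > 0.95 under Beta(1 + y, 1 + n - y). That probability is 0.969 at 3/4, 0.971 at 4/6 and 0.975 at 5/8. True rates are assumed; those below level 3 are 1/2/5/10%, or 1/2/3/5% in the first case.

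| True rates, levels 3/4/5 | Level 5 chosen: now | Rule 1 only | Both | DLTs per trial: now | Both | Level 3 chosen: now | Both |
|---|---|---|---|---|---|---|---|
| 10/20/50% | 57% | 60% | 42% | 5.1 | 4.7 | 6% | 7% |
| 15/30/45% | 58% | 60% | 48% | 5.0 | 4.7 | 11% | 16% |
| 20/35/50% | 43% | 46% | 35% | 5.4 | 5.1 | 18% | 25% |
| 15/20/25% (Table 4) | 94% | 94% | 88% | 3.1 | 3.0 | 1% | 4% |
| 15/20/30% | 89% | 90% | 82% | 3.6 | 3.5 | 2% | 4% |

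Under the current rules level 5 becomes the MTD, although its own data give Pr(rate > 30%) > 0.95, in 12%, 6% and 6% of trials in the first three cases, and in 1.5% at the Table 4 rates.

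**What the plan tested.** "Operating characteristics are calculated by BMA-CRMSimulator for two different scenarios". Table 4 sets levels 4 and 5 at 20% and 25%, Table 5 at 70% and 75%. Neither has level 4 near target and level 5 well above it.

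**The case against.** A CRM is meant to borrow strength across doses, and this one is standard. It does correct itself: 2/2 at level 4 does not escalate, 4/4 at level 5 steps down, and 1/2 at level 4 followed by 2/2 at level 5 returns to level 4 (0.308/0.359). A reader might infer that nothing protects patients at levels 4 and 5. The day-21 wait, the no-skip rule and these step-downs show otherwise.

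The 3/4 repeat rests on 0.302 under the closest-dose rule. Read as a cap on posterior means, the stated goal of 30% or lower would give level 4. That stands: the text supports both readings.

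A reader might also infer that 2/2 at level 5 would readily make it the MTD. It would not. Finishing with exactly 2/2 there and level 5 chosen has a probability below 0.001 in every case above.

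The toxic scenarios are assumptions. Section 13.2 shows no DLT in 21 patients across the arms, and levels 4 and 5 were added because plasma EGF had not risen, so under-dosing matters too. Part of the fall in level 5 selection goes to level 3. This also stands, and is why closing a level on 2/2 is not part of the fix.

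Finally, the counts are a snapshot. The 2019 amendment entry on vials for Arm 2B level 5 suggests, without proving, that the trial had moved on.

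**Conclusion.** The gap is real and follows from the plan's own model. From the printed counts, Arm 2B escalates to an untested dose straight after 1/2 DLTs. It repeats level 5 after 2/2, and after 3/4 under the closest-dose reading. The only phase I stop is nowhere near its threshold in these cases.

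The size is moderate. Both rules cut selection of a too-toxic level 5 by 8 to 15 percentage points and save 0.3 to 0.4 DLTs per trial. These gains rest on the assumed rates; the dose decisions do not. Rule 1 alone is a patient-protection measure: it costs nothing at the Table 4 rates and saves about 0.1 DLT per trial in the toxic cases, but raises selection of a too-toxic level 5 by 2 to 3 points. It therefore needs its companion.

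The documents do not show that any patient was dosed along these paths, because enrolment after the printed counts is unknown.

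**What to change.** In section 13.1, for Arm 2B:

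1. Do not escalate directly after a cohort with an observed DLT rate above 30% (1/2 or 2/2).
2. Close a level and all above it, for dosing and for MTD choice, when at least 3 patients treated there give Pr(DLT rate > 30%) > 0.95 under a uniform prior (for example 3/4, 4/6 or 5/8).
3. Say whether 30% or lower is a cap or whether the closest dose governs.
4. Rerun the operating characteristics from the current counts, adding a case with level 4 near target and level 5 well above it.

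This takes a few sentences and one simulation run, and no extra patients. The cost is that level 5 is chosen less often when it is acceptable (94% to 88% at the Table 4 rates, 89% to 82% if its rate is exactly 30%), with some shift to level 3 (11% to 16% and 18% to 25% in the second and third toxic cases).

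Rules 1 and 2 still allow one repeat after 2/2 at level 5. Whether to accept that is the sponsor's choice. Closing on 2/2 as well lowers level 5 selection in the toxic cases to 38%, 43% and 31%, but to 83% and 77% when level 5 is acceptable. Stepping the next cohort down one level after 2/2, without closing, keeps 88% and 82%, with 47%, 51% and 38% in the toxic cases.

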Dose	Actual probability in theory of having a DLT at each dose	Probability of Selecting the specified dose given the probabilities of having a DLT listed in the 2nd column	Estimated Number of subjects treated at each dose level during the study
125 USP hCG/875 pg EGF/m ²	0.25	0.28	6.7
250 USP hCG/1,750 pg EGF/m ²	0.30	0.29	3.1
500 USP hCG/3,500 pg EGF/m ²	0.40	0.23	5.3
1,000 USP hCG/7,000 pg EGF/m ²	0.50	0.07	2.6
2,000 USP hCG/14,000 pg EGF/m ²	0.60	0.02	0.7
3,500 USP hCG/24,500 pg EGF/m ²	0.70	0.00	0.2
5,000 USP hCG/35,000 pg EGF/m ²	0.75	0.00	0.1

Phase II extension: Studying the efficacy of hCG (Arm 1, Arm 2A and Arm 2B)

After completion of the dose finding trial for each arm, the final doses will be carried forward into a two-stage phase II extension trial to confirm safety and make a preliminary determination of the activity level for Arm 1 and Arm 2. If the phase I trial enrolls fewer than 13 patients at the MTD, we will employ Simon’s Minmax two-stage design (Simon, 1989) with the possibility to discontinue after the 1st stage if the response rate is low.

- **Stage 1:** Enroll a total of 12 patients (including all treated at the MTD in phase I). *If 5 or more of these respond, the trial will continue to stage 2.*

- **Stage 2:** Enroll an additional 14 patients. *If 14 or more out of 26 patients respond, hCG will be considered promising for further investigation.*

If phase I trial enrolls more than 12 patients at the MTD, we will adjust the futility rule above for the two stage design with the giving number of patients enrolled at the MTD.

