For Arm 2B, same as the other two arms, if fewer than 13 patients are enrolled at the MTD, the phase II extension trial using Simon's two-stage Minmax design will require 26 patients to test the null hypothesis that the response rate at day 28 is <40% versus the alternative that the response rate is $\geq 65\%$ after assuming 80% power and a significance level of 0.05 and using a maximum of 26 patients. We expect that for each arm, phase I and II will require approximately 37 patients due to use of patients from the phase I trial in the phase II extension ([table 4](#) shows about 9 patients will be treated under MTD). But the sample size could be as high as 44 when only two patients were treated at MTD in phase I. We expected the sample size of phase I/II study for Arm 2B will be 37 to 44 patients.

The number of evaluable patients per year will be approximately 20 for each arm. We expect accrual to be completed within 7 years.

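### With 12 or fewer patients at the MTD, the printed phase II limits (5 of 12, then 14 of 26) have a type I error of 0.104, not the stated 0.05.

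*Combined protocol and SAP*

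**What the plan says.** Section 13.1 (Phase II extension) sets the rule for each arm, under the condition "If the phase I trial enrolls fewer than 13 patients at the MTD". Stage 1 has 12 patients, counting those treated at the MTD in phase I: "If 5 or more of these respond, the trial will continue to stage 2". Stage 2 adds 14 patients: "If 14 or more out of 26 patients respond, hCG will be considered promising for further investigation". The same two limits appear in the synopsis (study design and Enrollment Plan), in the schema after it, and in Section 4 for each of the three arms.

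Section 13.2 gives the design inputs: a null response rate below 40% at day 28, an alternative of 65% or more, "after assuming 80% power and a significance level of 0.05 and using a maximum of 26 patients". They are given for Arms 1 and 2A and repeated for Arm 2B. For Arms 1 and 2A it adds: "We will choose the rule that minimizes the expected sample size giving a true response rate equivalent to the null hypothesis".

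For more than 12 patients at the MTD, Section 13.1 says only that "we will adjust the futility rule above for the two stage design with the giving number of patients enrolled at the MTD".

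On which case to expect, Section 13.2 says that Table 2 "shows about 13 patients will be treated under MTD" (Arms 1 and 2A) and that Table 4 "shows about 9 patients will be treated under MTD" (Arm 2B).

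**The concern.** The limits and the error rates describe the same test, so one should follow from the other. A Simon design is usually tabulated by the largest count that fails: stop with r1 or fewer responders, and do not reject the null with r or fewer. If r1 = 5 and r = 14 are written out as the smallest counts that pass, both limits end up one response too low. The documents do not say how the limits were obtained, and the finding does not depend on that explanation.

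This is the go/no-go rule for the phase II primary endpoint. If the limits are too low, an inactive arm is carried forward more often than readers are told, and the early stop that should protect patients in an inactive arm works less often. Exactly 5 of 12 or exactly 14 of 26 would lead to the opposite decision from the design that Section 13.2 describes.

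**Working it through.** **Inputs.** From Section 13.2: p0 = 0.40, p1 = 0.65, level 0.05, power 0.80, maximum N = 26. From Section 13.1: n1 = 12, n2 = 14, continue if X1 ≥ 5, promising if X1 + X2 ≥ 14. The plan does not state sidedness. I take the level as one-sided because the hypotheses are directional. Phase I patients at the MTD are treated as ordinary binomial observations, as the plan does.

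**Formula.** With continuation limit a and final limit c,

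P(promising | p) = Σ over x = a,…,12 of P(Bin(12, p) = x) × P(Bin(14, p) ≥ c − x).

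**Printed rule (a = 5, c = 14) at p = 0.40**

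| x of 12 | P(X1 = x) | P(X2 ≥ 14 − x) | product |
|---|---|---|---|
| 5 | 0.2270 | 0.0583 | 0.0132 |
| 6 | 0.1766 | 0.1501 | 0.0265 |
| 7 | 0.1009 | 0.3076 | 0.0310 |
| 8 | 0.0420 | 0.5141 | 0.0216 |
| 9 | 0.0125 | 0.7207 | 0.0090 |
| 10–12 | | | 0.0025 |

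The unrounded products sum to 0.1039. The same sum at p = 0.65 gives power 0.9073. The stated 0.05 is not reproduced.

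**What the stated inputs lead to.** I searched all two-stage designs for p0 = 0.40 and p1 = 0.65 with type I error at most 0.05 and power at least 0.80.

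- No design with fewer than 26 patients qualifies, so the plan's maximum of 26 is reproduced.
- At N = 26, 16 designs qualify, and all 16 have a final limit of 15. None qualifies with a limit of 14, and a limit of 16 never reaches 80% power.
- The one with the smallest expected N under the null has n1 = 12, continues with at least 6 and declares promise with at least 15. The plan's stage sizes match it; both of its limits are one lower.

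**Comparison.** Early stopping under the null is P(Bin(12, 0.40) < a), and expected N is 12 + 14 × (1 − early stopping).

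| Continue / promising | Type I error | Power | Early stop at 40% | Expected N at 40% |
|---|---|---|---|---|
| ≥5/12, ≥14/26 (printed) | 0.1039 | 0.9073 | 0.438 | 19.9 |
| ≥6/12, ≥15/26 | 0.0469 | 0.8086 | 0.665 | 16.7 |
| ≥5/12, ≥15/26 | 0.0508 | 0.8336 | 0.438 | 19.9 |
| ≥6/12, ≥14/26 | 0.0906 | 0.8694 | 0.665 | 16.7 |

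Changing one limit alone does not bring the error to 0.05. The expected extra exposure under the null is 19.87 − 16.69 = 3.2 patients per affected arm.

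**Other readings.** With no futility look, 14 of 26 gives 0.108. A two-sided 0.05 would allow only 0.025 in the upper tail. A level of 0.10 would also be exceeded, and would lead to a minimax design with N = 19. The printed rule has level 0.05 only if the null rate is about 0.364.

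**More than 12 at the MTD.** The plan gives no final limit or maximum N for this case. Assume that 14 of 26 is kept and only the futility limit moves. Then, for first stages of 13 to 20, every futility limit that keeps 80% power gives a type I error between 0.062 and 0.108. Adjusting the futility limit alone therefore cannot reach 0.05.

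**The case against.** The strongest case concerns reach and weight, not the arithmetic.

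- **Reach.** The printed rule may not be used in every arm. The table in Section 13.2 shows Arm 1 with 6 patients at level 3 and 10 to enroll, and Arm 2A with 3 at level 3 and 16 to enroll, all without a DLT. If level 3 takes everyone who remains, they reach 6 + 10 = 16 and 3 + 16 = 19, and the other branch applies. Arm 2B has 13 to enroll with the next 2 at level 4, so at most 11 can be at level 5; the printed rule applies there if level 5 becomes the MTD. This stands as a limit on scope, but it depends on later DLTs, and the 12.7 patients that Table 2 expects at the top dose straddle the cut-off.
- **The other branch.** Section 13.2 states 0.05 and 80% only for fewer than 13 patients at the MTD. For more than 12, the fault is an incomplete rule, not a contradicted figure. This is right, and the range of 0.062 to 0.108 is conditional on the assumption given with it.
- **Weight.** Phase II is described as preliminary, and power is higher than planned. Both are true. Neither makes the stated level correct.
- **Timing.** Stage 1 counts patients already treated in phase I, so raising the limits now could follow observed responses. This is a fair caution, and the amendment should deal with it.

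**Conclusion.** The concern holds. For an arm with 12 or fewer patients at the MTD, the printed rule has a one-sided type I error of 0.104 against the stated 0.05, with power 0.907 against the planned 0.80. Under a true rate of 40%, early stopping is 0.438 instead of the 0.665 of the design that the stated inputs produce. The result rests on exact binomial probabilities at 40% and 65%; a two-sided reading would widen the gap. Power is not lost: the fault is a go/no-go rule that does not have the error rate claimed for it. For more than 12 at the MTD, the plan does not fix the final limit, and keeping 14 of 26 could not meet 0.05 with 80% power.

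**What to change.** Change both limits in all seven places: synopsis study design, synopsis Enrollment Plan, schema, Section 4 for each of the three arms, and Section 13.1. New rule: continue to stage 2 if at least 6 of 12 respond; promising if at least 15 of 26 respond.

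Alternatively, keep the printed limits and restate both sample-size paragraphs of Section 13.2 with significance level 0.104 and power 0.907.

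For more than 12 patients at the MTD, state that the final limit is recomputed together with the futility limit, and give the maximum N. If that stays at 26 with a final limit of 15, these first-stage limits meet both 0.05 and 80%:

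| Continue with at least | Type I error | Power |
|---|---|---|
| 6 of 13 | 0.0498 | 0.828 |
| 7 of 14 | 0.0480 | 0.818 |
| 8 of 15 | 0.0452 | 0.802 |
| 8 of 16 | 0.0491 | 0.825 |
| 9 of 17 | 0.0470 | 0.814 |
| 10 of 19 | 0.0487 | 0.825 |
| 11 of 20 | 0.0463 | 0.814 |

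For 18, no limit meets both: 9 of 18 gives 0.0502 and 0.831, and 10 of 18 gives 0.0438 and 0.797.

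The amendment should record whether day 28 responses at the candidate MTDs were known when the limits were changed.

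Cost: a wording amendment and no extra patients. With the higher limits, power falls from 91% to 81%, still above the planned 80%.

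### The printed phase II rule (at least 5 of 12, at least 14 of 26) has a type I error of about 0.10 in all three arms, not the stated 0.05, and the rule that Arms 1 and 2A will very probably need has no numbers

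*Combined protocol and SAP*

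**What the plan says.** The synopsis, section 4 and section 13.1 give the same phase II rule for every arm. Stage 1 has 12 patients, counting those treated at the MTD in phase I, and continues with 5 or more responders. Stage 2 adds 14, and "If 14 or more out of 26 patients respond, hCG will be considered promising for further investigation". The rule applies when fewer than 13 patients were treated at the MTD in phase I. Above 12, the only instruction is "we will adjust the futility rule above for the two stage design with the giving number of patients enrolled at the MTD".

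Section 13.2 gives the basis for the rule. It tests "the null hypothesis that the response rate at day 28 is <40"% against 65% or more, "after assuming 80% power and a significance level of 0.05 and using a maximum of 26 patients". It adds that the rule chosen will minimise the expected sample size under the null.

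The same section tabulates phase I progress. Level 3 is the top dose in Arms 1 and 2A. Arm 1 shows "Level 3: N = 6, DLT = 0", with 10 more to enrol. Arm 2A shows 3 patients at level 3 without a DLT, with 16 more to enrol. In both arms the next cohort goes to level 3. On sample size it concludes: "Therefore we expect the sample size of the phase I/II study for Arm 1 and Arm 2A will be 66 to 88 patients".

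**The concern.** The phase II rule decides whether hCG is called promising in each arm. If its cut-offs do not deliver the stated error rate, an inactive regimen is declared promising more often than the plan tells its readers. In two arms the 12-patient look is also likely to be replaced by a rule without a stage 1 cut-off, a final cut-off or error rates. The trial has no concurrent control, and the plan does not say when that rule will be fixed.

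**Working it through.** **Inputs (section 13.2).** p0 = 0.40, p1 = 0.65, error 0.05, power 0.80, N = 26. Sidedness is not stated; I take it as one-sided, as is usual for Simon designs.

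**Formula.** With first stage n1, continuation at a1 or more responders and success at a or more of 26:

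P(promising | p) = Σ over x from a1 to n1 of P(Bin(n1, p) = x) × P(Bin(26 − n1, p) ≥ a − x).

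The error is this sum at p = 0.40 and the power is the sum at p = 0.65.

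**Step 1: the plan's own design.** A search for the smallest N meeting 0.05 and 80% returns n1 = 12 and N = 26, so the sample sizes reproduce. The cut-offs do not:

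| Rule | Error | Power |
|---|---|---|
| Printed: ≥5/12, ≥14/26 | 0.104 | 0.907 |
| Single stage: ≥14/26 | 0.108 | 0.917 |
| Minimax: ≥6/12, ≥15/26 | 0.0469 | 0.809 |

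Simon designs are commonly written as stop at r1 or fewer and reject at r or fewer. Here r1 = 5 and r = 14. Writing those numbers as the minimum needed to continue or succeed gives the printed rule, so an off-by-one is the likely cause. It also weakens the futility look: the chance of stopping at stage 1 under the null is P(X ≤ 4 of 12) = 0.438 as printed, against P(X ≤ 5 of 12) = 0.665 in the minimax design. The expected sample size under the null is 12 + 14 × (1 − 0.438) = 19.9 as printed and 12 + 14 × (1 − 0.665) = 16.7 in the minimax design. A one-sided 0.025 reading would need N = 32, so it does not explain the printed figures.

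**Step 2: which branch applies.** If all remaining phase I patients are treated at level 3, Arm 1 ends with 6 + 10 = 16 there and Arm 2A with 3 + 16 = 19. Both exceed 12. I simulated the plan's CRM from these counts (power model, prior variance 2, skeleton 1/2/5/10/20%, target 25%, cohorts of 2, true rates equal to the skeleton, 2,000 runs, without the 0.90 safety stop). At least 13 patients were at the MTD in about 99% of runs in Arm 1 and 92% in Arm 2A. The plan's own expectation of about 13 at the MTD in these arms already falls in the branch without numbers. In Arm 2B the plan expects about 9, so there the printed 12-patient rule would be used.

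**Step 3: can an adjusted futility cut rescue 14 of 26?** Every stage 1 cut was tried for n1 = 13 to 20; none gives both error ≤0.05 and power ≥80%. At the two counts of interest:

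| n1 | Stage 1 cut | Error | Power |
|---|---|---|---|
| 16 | ≥8 | 0.095 | 0.889 |
| 16 | ≥9 (lowest error with 80% power) | 0.072 | 0.820 |
| 16 | ≥10 | 0.041 | 0.682 |
| 19 | ≥10 | 0.090 | 0.883 |
| 19 | ≥11 (lowest error with 80% power) | 0.062 | 0.804 |
| 19 | ≥12 | 0.031 | 0.664 |

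**Step 4: the same check with 15 of 26.**

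| n1 | Stage 1 cut | Error | Power |
|---|---|---|---|
| 12 | ≥6 | 0.0469 | 0.809 |
| 13 | ≥6 | 0.0498 | 0.828 |
| 14 | ≥7 | 0.0480 | 0.818 |
| 15 | ≥8 | 0.0452 | 0.802 |
| 16 | ≥8 | 0.0491 | 0.825 |
| 17 | ≥9 | 0.0470 | 0.814 |
| 18 | ≥9 | 0.0502 | 0.831 |
| 18 | ≥10 | 0.0438 | 0.797 |
| 19 | ≥10 | 0.0487 | 0.825 |
| 20 | ≥11 | 0.0463 | 0.814 |

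Only n1 = 18 has no cut that meets both targets.

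**Step 5: totals.** The plan's figures reproduce: 20 + 26 − 13 = 33 and 20 + 26 − 2 = 44 per arm, hence 66 to 88 for two arms. With 16 and 19 at the MTD the totals are 20 + 26 − 16 = 30 and 20 + 26 − 19 = 27, or 57 together.

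**The case against.** The strongest defence concerns the adjusted branch. Section 13.2 fixes both response rates, the error, the power, the maximum of 26 and a selection criterion. Read as covering larger first stages, those conditions lead to a single stage 1 cut with 15 of 26 at each n1 from 13 to 20 except 18. The number treated at the MTD is driven by toxicity, not response. On that reading a printed table and a date are missing, rather than a principle. This stands in part: the criterion follows the sentence on fewer than 13 patients, so extending it is a reading; it gives no answer at 18; and it leads to 15 of 26, which the plan does not print. It does not touch the base rule, whose error is 0.104 by direct calculation.

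A reader might infer several stronger points that the documents do not support:

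- *The 12-patient look will not apply in Arms 1 and 2A.* Later DLTs could leave fewer than 13 at the MTD, and the plan allows for as few as 2.
- *14 of 26 cannot hold 0.05.* A harsh enough futility cut does so, at 66 to 68% power for n1 = 19 and 16. The failure is against 0.05 and 80% together.
- *14 of 26 is retained in the adjusted branch.* Only the futility rule is said to change. Retention is implied, not stated.
- *The adjusted rule will be set after responses are seen.* The plan gives no timing in either direction.
- *57 is the expected total.* It is a best case. The table of counts is undated, and section 6.4 requires 3 doses for phase I evaluability but 6 for response assessment in Arm 2A, so some phase I patients may not count towards stage 1.

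**Conclusion.** The point holds for all three arms. As printed, a regimen with a true 40% response rate would be called promising with probability 0.104, about twice the stated 0.05; the power is 0.907 rather than about 0.80. This rests only on the plan's rates and cut-offs and on a one-sided test.

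For Arms 1 and 2A, the branch that will very probably apply has no numeric rule. That likelihood assumes the tabulated counts and DLT rates no worse than the skeleton. If 14 of 26 is kept there, the lowest error compatible with 80% power is 0.072 at 16 patients and 0.062 at 19. The base cut-offs are an error to correct; the adjusted branch is an omission to fill. The lower sample size figure of 66 is a minor inconsistency with the table in the same section.

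**What to change.** 1. In the synopsis and sections 4, 13.1 and 13.2, change the rule for all arms to continue at 6 or more of 12 and promising at 15 or more of 26. State the test as one-sided, with exact error 0.047 and power 0.809.
2. Replace the sentence on adjusting the futility rule with a fixed table, with success at 15 or more of 26 and these minimum stage 1 responders: 6 for n1 = 13; 7 for 14; 8 for 15 or 16; 9 for 17; 10 for 19; 11 for 20. For n1 = 18 choose one cut and print its exact figures: 10 (0.044, power 0.797) or 9 (0.0502, power 0.831).
3. Fix the table before responses at the MTD are tabulated, and define n1 as patients evaluable for response under section 6.4.
4. Restate the lower end of the Arm 1 plus Arm 2A total as about 57, conditional on all remaining phase I patients being treated at level 3 and evaluable for response. Keep 88 as the upper end.

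The cost is one more responder needed for success, and power of about 80%, as the plan states, instead of the 91% that the printed rule delivers. No patients are added.
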